**2.5 What are the planned inclusion/exclusion criteria?**

Recruitment of university students will occur at multiple centres. Volunteer couples must (1) not have been vaccinated against HPV (both partners); (2) plan on remaining in Montreal for at least 1 year; (3) be in a new relationship that started no more than six months prior to study entry; (4) plan on having continued sexual contact with partner; (5) have no history of cervical, penile, oral or anal cancers; (6) not be pregnant or plan on immediately becoming pregnant, and (7) be willing to comply with study procedures. Study forms will be based on the co-applicants' experience with their previous molecular epidemiologic studies of HPV infection (please see section 2.11 for details). Concerning requirements 3 and 4 above, we will screen couples based on the Dyadic Adjustment Scale (DAS) (please see appendix) as a validated instrument to measure the stability of couples' relationships. It includes 4 scale questions that gauge the degree of confidence in

[figure not shown]
the partner, likelihood of a separation, and overall satisfaction with the relationship. Couples in which one of the partners scores at less than 80% of the maximum score will not be enrolled.

### **2.6 What is the proposed duration of treatment period?**

Participants will be provided three doses of Gardasil or Havrix at enrolment (time 0), and at 2 and 6 months. After month 12, a crossover of the intervention will take place, as well.

### **2.7 What is the proposed frequency and duration of follow up?**

HPV infection status will be measured at enrolment (time 0), and at 2, 4, 6, 9, and 12 months (Figure 1). A one-year follow-up period was chosen to allow sufficient opportunity for HPV infection transmission (in our HITCH cohort study of couples most transmission events occur within that period). Longer follow-up would likely result in substantial attrition.

**Figure 1: Study design and schedule of procedures**

## 2.8 What are the proposed primary and secondary outcome measures?

The primary outcome will be the reduction of HPV DNA positivity for the target HPV vaccine types (i.e., HPVs 6, 11, 16, and 18) in multiple anatomic sites in Havrix-treated sexual partners of persons who received Gardasil. These are the combinations  $M^T F^P$  and  $M^P F^T$  in table 1. The main control group for unhindered HPV transmission will be group  $M^P F^P$  and the full protection control group is represented by the combination  $M^T F^T$ .

We will measure prevalence and incidence of HPV 6, 11, 16, and 18 infections (via DNA detection by the PCR protocol described below) in all three samples (vaginal, anal, and oral, for women, and penile, anal, and oral, for men) for the above time points among all subjects. Specimens for all three sites will be collected during all six clinic visits.

We will not exclude subjects if they are positive for HPV DNA of HPVs 6, 11, 16, and 18 because we intend to verify whether protection conferred by vaccination (both self and partner's) extends to mucosal sites that have not yet been infected by the above target types. Actually, prevalent infections at enrolment will be informative because they could be the source of a transmission event to a partner.

Reduction in HPV type concordance (for the four target types) will be the main outcome evaluable as per the above group contrasts. These comparisons will be done with due attention to the enrolment virological status of the individuals. For instance, we expect that a Havrix-treated woman who is positive for HPV 6 in the anal specimen but negative for this type in the vaginal specimen may derive benefit if her partner receives Gardasil, even if he is HPV-6 positive in the penile sample. Our assumption is that protection via vaccination is pan-mucosal, via transudation of neutralizing antibodies; this protection may mediate transmission.

## 2.9 How will the outcome measures be measured at follow up?

### *Data collection and follow-up*

Figure 1 shows the study design and schedule of procedures. Assessing pre-enrolment humoral immune response to HPV infection will be done by withdrawing 10 ml of blood from all study participants and testing serum samples with a competitive Luminex immunoassay (CLIA) for detecting any antibody response and quantifying it. CLIA testing will be done by Merck Research Laboratory at Merck's Headquarters in Pennsylvania, USA, at no cost to the study. CLIA testing will measure neutralizing antibodies and thus will provide valuable insights to help us understand initial transmission events. We will also maintain serum samples at -70°C for future serological studies with polyclonal anti-HPV assays. Funding for such studies will be sought at the renewal stage of this investigation so as to avoid unduly increasing costs for the current budget.

The most important outcome is measurement of HPV infection status (via HPV DNA testing) in both partners. They will be done at 0, 2, 4, 6, 9, and 12 months. Samples will be collected at three sites: penile/vaginal, anal, and oral for men and women at every visit. Anal and vaginal samples will be self-collected at the clinic, after properly instructing participants. The rest of the samples will be collected by specially trained study nurses, at every visit. The nurse will collect a sample of exfoliated cells from representative sites in the oral cavity using a toothbrush and a mouthwash. This method has been shown to yield good quantities of DNA for testing. Oral samples will be immersed and suspended in phosphate-buffered saline.

Previous research on the method of penile skin swabbing to detect HPV DNA has proven this method to be reliable. All samples will be placed in a -20°C freezer pending transfer to [name] laboratory where they will be stored at -70°C until being tested. HPV DNA testing will be done by the PGMY linear array PCR method, which permits typing and has been extensively validated in our molecular epidemiologic studies of HPV infection.

#### *Collection of vaginal specimens*

Self-collected vaginal specimens will be obtained at months 0, 2, 4, 6, 9 and 12, resulting in six specimens in total (Figure 1). Women would be asked to abstain from intercourse a minimum of 48 hours before collection of the specimen. This will minimize the risk of contamination with residual male epithelial cells, urethral secretions, and/or semen.

Self-collection methods have been shown to be valid for research and clinical purposes, and acceptable to women. Feasibility studies done in our group prior to the HITCH study and during the summer 2012 (appendix) showed that although participants prefer to have their specimens collected by the nurse, they were also comfortable with the self-collection approach, if taught by the study nurse. They also found that self-collection was more practical for multiple specimens collected during the course of the study.

The instructions for self-collection of vaginal specimens will follow those of the validated protocol of Gravitt et al.. Women will be instructed to remove clothes from the waist down, remove the swab from the wrapping, and choose a comfortable position (either standing with one foot on a stool, toilet, or bathtub, or standing with legs apart and knees slightly bent). They will be told to relax and insert the cotton tip of the swab into the vagina, without touching the labia or urethra. The swab is to be gently pushed up into the vagina until physically it cannot go any further. This will be followed by a motion using the thumb and two fingers to remove the swab halfway out of the vagina, and then re-inserting it. The swab is to be rotated 3 times inside the vagina, while kept as far into the vagina as possible. The subject will then withdraw the swab holding the lips of the labia apart taking care not to touch other portions of the genitals. The swab will be placed directly into the plastic vial with the liquid preservative (Universal Collection Medium [UCM], Qiagen®, Gaithersburg, MD) that will be provided. UCM adequately preserves exfoliated specimens for DNA, RNA, and protein analyses.

#### *Collection of Male penile skin swabs*

Men will provide penile skin swab specimens for HPV testing on all aforementioned six study visits (Figure 1). Previous research and our own experience in the HITCH study has indicated that men are very willing to submit to painless penile skin swabbing and that this method of sampling yields adequate material for HPV DNA detection compared to urine and urethral specimens. In the feasibility study, 64% (9/14) said that this procedure would not prevent them from participating. Men will be asked to abstain from sexual intercourse for 48 hours preceding collection to reduce the possibility of detecting HPV carriage from residual female secretions.

The research nurse will conduct an external examination of the genital area to note circumcision status, and the presence of any relevant clinical findings (e.g., warts, lesions, erythema, abrasions, inflammation, discharges, tenderness, adenopathy). Exfoliated cells will be collected by swabbing vigorously with a Dacron™ applicator moistened with sterile normal saline. The nurse will use a new wet swab and sweep 360° around the coronal sulcus and then another 360° around the glans penis. The nurse will use a new wet swab to sample the entire skin surface of each of the quadrants

of the shaft of the penis (left and right ventral, and left and right dorsal). Each swab will be placed into an individual UCM-containing collection vial and labelled according to the anatomic source.

*Collection of anal swabs* (Added 09-June-2017: refer to the first page of the protocol and to appendix 1 for justification of dropping anal sampling)

All study participants (both genders) will provide anal swab specimens for HPV testing on all six study visits (Figure 1). Lampinen et al. developed feasible, simple illustrated instructions for self-collecting anal swabs. Study participants will be instructed to remove clothes from the waist down, remove the swab from the wrapping, and choose a comfortable position, e.g. by standing with one foot on a stool, to facilitate access to the anus. The subject will be asked to hold one buttock to one side. Then the subject will hold the swab 3-4 cm from the tip. They will have to hold the swab firmly and gently insert it into their anus (3-4 cm) until the tips of their fingers touch the outside of their anus. They will need to release their hold on the shaft, then take hold of the swab again, about halfway down the shaft. The swab is to be moved once in a large circle, pressing gently against the inside of their anus. Then the swab will be, slowly and gently, removed from their anus and turned slowly as they remove it. The swab will then be placed into a UCM-containing collection vial.

*Self-administered web-based questionnaire (please see appendix)*

We will use a secure, confidential study-designated Internet site to provide participants with protected access to the web-based questionnaire by assigned login names and passwords. At induction, males and female subjects will learn to use the web-based system using computers at the clinic sites. At that time they will complete their enrolment questionnaire. Subsequently, all participants will complete five follow-up questionnaires (months 2, 4, 6, 9 and 12).

*Randomization Strategy*

Eligible couples will be recruited into each centre and treatment assignment will apply to a couple as a unit. Randomization of the study participants will be done via a computer-assisted block randomization with randomly variable block sizes at the coordination centre at McGill University. Treatment assignment will be given to the study coordinator at a centre via a secure web-based program at the time the couple is enrolled. To ensure participant blinding, vaccine vials will be masked and look identical so that both the participant and the nurse administering the vaccine will be unaware of their content. This will also ensure that both partners will not know whether they have received Gardasil or Havrix.

**2.10 Will health service research issues be addressed? Justify inclusion/exclusion of health economics and quality of life measures. If these measures are to be included full details should be given including power calculations.**

Health service research issues will not be directly addressed by the proposed study. However, should our trial demonstrate efficacy, its findings will be instrumental in orienting initial estimates of cost-effectiveness by our team or others. Our CIHR Team on HPV-associated diseases includes a health economist, [name], at Laval University. The results of this trial will assist in future analyses by [name]. Detailed information to inform future cost-utility analyses will be collected during the trial and will be made available to [name] (please see his letter).

**2.11 What is the proposed sample size and what is the justification for the assumptions underlying the power calculations? It is important to give the justification for the size of the difference that the trial is powered to detect. Does the sample size calculation take into account the anticipated rates of non-compliance and loss to follow-up given below?**

*Statistical power*

Empirically-based estimates of parameters for sample size calculation were obtained from our unit's molecular epidemiologic investigations of HPV infection of female university students, i.e., the McGill-Concordia cohort study and the "HPV Infection and Transmission among Couples through Heterosexual activity" (HITCH) cohort study, both funded by CIHR. The HITCH study is the same recruitment platform that will serve TRAP-HPV. Prevalence of the four Gardasil preventable HPV types (6,11,16, & 18) at enrolment was 23% and comparable between genders. The rate of acquisition of any of these types was 3.8 per 100 subject-months, which translates to approximately 40% cumulative incidence for these types in the unvaccinated HITCH population. The latter is the most empirically valid expectation for the rate of transmission events in cell  $M^{TF^P}$  in table 1. Therefore, the latter group provides the baseline comparison for the two groups in table 1 with vaccination-discordant regimens,  $M^{TF^P}$  and  $M^{PF^T}$ , whereas the concordant group with both partners receiving Gardasil ( $M^{TF^T}$ ) serves as a secondary control group where minimal transmission is expected to occur.

We used the Bernstein and Lagakos approach to derive sample size projections for different levels of power (80% and 90%), with type one error of 0.05, and one-sided hypothesis for reductions in the above rate of transmission varying between 30% and 70%, i.e., the expected magnitude of the protective effect in the discordant vaccination groups where the partner receiving placebo is the one to be protected. We also assumed gender equivalent rates of transmission as per our findings in the HITCH study. At 80% power we would require 97 couples per group (cells in table 1) to detect a significant 40% reduction in transmission of vaccine-targeted types. A group size of 80 couples per group would be required to attain 90% power to detect a 50% reduction. The latter can be statistically detected with as little as 59 couples per group if we relax power to 80%. Evidently, larger effect sizes will have reduced requirements. There are no published empirical estimates of the expected level of transmission reduction, but our informal consultation with experts in the field, including [name], a member of our Steering Committee (see below), indicates that 40%-50% reduction in transmission is a conservative estimate for the protective effect to a partner of a vaccinated individual.

HITCH, the closest recruitment platform that TRAP-HPV will be based on, has a cumulative 16% loss to follow-up at month 12, which translates to a per-visit attrition rate of 2.7%. By applying the same expectation of losses to follow-up and using the most stringent definition of projected sample size (at 90% power and 40% effect size), we therefore propose to enroll 125 couples per group for a total of 500 couples. It is noteworthy that vaccine efficacy against HPV infection can occur with only two and even one dose. As we have observed in HITCH, the prevalence of vaccine-preventable types at enrolment is 23% and most transmission events occur early. Therefore, analyses of prevention of transmission events will begin to be informative from the second (2 months) visit and beyond.

**2.12 What is the planned recruitment rate? How will the recruitment be organized? Over what time period will recruitment take place? What evidence is there that the planned recruitment rate is achievable?**

Our team has developed considerable experience in recruiting female and male university students via our multiple epidemiological studies of HPV infection in Montreal. We are confident that based on our past rate of accrual (obtained with the HITCH study, which has the same characteristics of TRAP-HPV and just completed accrual of 500 couples very successfully) we can recruit 125-135 couples per year, which would permit accruing the complete sample of 500 couples in 4 years. Based on our previous epidemiological studies, such as HITCH, we expect excellent retention in our study (per visit attrition of 2.7%). Participants will also be given a monetary incentive at every visit to ensure their continued participation in our study. Individuals will be given \$500 (\$1000 per couple) as a cash incentive for their participation, if all study visits were completed. Remuneration will be distributed as follows: \$120 at enrollment visit, \$60 for each of the three subsequent visits, \$80 at visit 5, and \$120 at the last visit.

**Recruitment:** Our base for recruitment will be the McGill and Concordia University Health Services Clinics, which provide medical care year-round to students. Our team has conducted three studies among women attending these clinics since the late 90's. We have developed an excellent collaboration with the directors and staff of the student health services of both universities and we have been given ample office and clinic space there to manage our study subjects. We have a team of enthusiastic interns who serve as recruiters and have developed a good knowledge of campus life to identify study volunteers. Recruitment will be bolstered through campus-wide appeals, including posted notices, e-mails to student lists, etc. Additional efforts include mail-outs to students living in residence, presentations to students in professional schools, and information booths at student activities. Word-of-mouth will also be used for 'snowball' sampling. Also, given our 13-year experience recruiting subjects in university settings and that recruitment resources are already in place, we do not anticipate any major issues with recruitment.

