**History of protocol amendments approved by McGill University's Research Ethics Board**

(Refer to Appendix 1):

- Recruitment age increased from 18-26 years to 18-40 years (approved April 14, 2014).
- Maximum duration of relationship increased from 3 to 6 months (approved April 30, 2014).
- Compensation increased from CAD 350 to CAD 500 per couple (approved February 9, 2015). The above protocol changes were made to improve recruitment and/or simplify the logistics of the study.
- Gardasil 9 as intervention vaccine: The additional amendment relating to Gardasil 9 will enhance the health benefit of the study to participants while making this protocol truly cutting-edge with respect to the state of HPV science (approved July 08, 2015).
- Recruitment age increased from 18-40 years to 18-45 years (approved February 16, 2016).
- Discontinuing anal sampling: potential and current participants have confirmed our suspicions that troubling recruitment rates are due partially to the embarrassing and uncomfortable nature of this procedure (approved July 14, 2016).
- Adding a recruitment site in New York to increase the rate of accrual of participants (approved April 3, 2017).
- Compensation increase from CAD 500 to CAD 1000 per couple (approved May 8, 2017)
- Switch the placebo vaccine from Havrix to Avaxim (requested June 4, 2018, approved June 12, 2018).
- Second Oral Tube Collected: [name] transfers the sample to a freezer tube with tampon (she calls it "TE") - [name] removes the residues of the mouthwash and re-suspends it in the tampon. It's all kept in the freezer at [name] lab (information collected with [name] on February 11, 2022).
- Close study recruitment at 188 couples instead of the original 500 couples (requested on March 31, 2022, approved on May 26, 2022)
- Use of a different assay for serology testing (requested on September 8, 2022, approved on September 12, 2022) (Refer to Appendix 2)

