**2.13 Are there likely to be any problems with compliance? On what evidence are the compliance figures based?**

Although TRAP-HPV is complex in design and number of procedures, we are confident that there will be high compliance because of our inclusion and exclusion criteria, which will select only highly motivated couples (see section 2.5). Management will be done by a team that is highly experienced in conducting studies of HPV infection in couples. Participants will be administered the intervention at the clinic and attend follow-up visits much like the ones in our previous studies, such as the most recent HITCH study, which was successful in terms of retention and in maintaining constant contact with the couples. In any case, our sample size calculations took the anticipated losses into consideration.

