Cumulative risk models may be fitted with type-specific transmission as an outcome. GEE models can be used to incorporate data across multiple types of HPV, which is an alternative approach for incorporating repeated HPV prevalence data across HPV types and across visits involving the same woman). In a single Generalized Estimating Equations (GEE) logistic regression model, we can treat type-specific infection events for each of the four different HPV types as separate transmission endpoints and then estimate the exposure effect on selected HPVs as a group, as we have published recently. Mixed-effects models will also be adopted for incorporating repeated HPV transmission data across HPV types and across visits involving the same subject.

Although they will be screened as per the likelihood of their stability, if couples break-up and end their relationship before their last visit, they will be censored of the study while still contributing follow-up time and visits with informative specimens. As mentioned above, vaccination protection is expected to begin as early as the first dose, thus even with a subset of visits for a few couples, we can expect to analyze reductions in transmission before the full set of visits is completed.

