**Close recruitment early**

Recruitment in the TRAP-HPV study has been a challenge, and more so since the start of the COVID-19 pandemic. We had to cease study-related activities (mostly occur among student populations) from March 13 to June 2020 under the COVID-19 lockdown measures announced by the Quebec Government and by extension the McGill Research and Graduate Studies Offices at the Faculty of Medicine and Health Sciences. We resumed research activities on July 28, 2020, but most student populations continued online learning. Study recruitment continued to be a challenge; only 19 new couples were recruited over the last two years.

In order to maintain the scientific value of the TRAP-HPV study as well as allocate the remaining study funds to test the collected biological samples and pay the remuneration for all pending study visits, we are:

- 1- Closing recruitment as we will never be able to reach the target sample within a reasonable timeframe. The last couple was recruited on February 16, 2022.
- 2- Completing the follow-up of existing couples. However, we are proposing to eliminate Visit 6 and stop follow-up at Visit 5 (one assessment point post-vaccination with the third dose of the vaccine). By design, six study visits are scheduled over a one-year period (at enrollment [month 0], and at 2, 4, 6, 9, and 12 months) and the vaccines are administered at three visits (0, 2, and 6 months). We anticipate by this to complete the study by

November 2022 (rather than February 2023 if we were to keep Visit 6). However, because of the usual delays for students to adhere with the expected date of appointments keeping Visit 6 will actually impose an inordinately long study duration.

For couples who will not have a visit 6, compensation will be modified to \$100/person (\$200/couple) instead of \$80/person (\$160/couple) for Visit 5.

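### 125 couples per group does not give 90% power for a 40% reduction after 16% loss: the plan's own figures imply about 83–86%, and 88% with no losses at all

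*Combined protocol and SAP*

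**What the plan says.** Section 2.11 (Statistical power) uses the Bernstein and Lagakos approach with a one-sided type I error of 0.05. It gives three requirements per cell of Table 1:

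- 40% reduction, 80% power: "At 80% power we would require 97 couples per group (cells in table 1) to detect a significant 40% reduction".
- 50% reduction, 90% power: "A group size of 80 couples per group would be required to attain 90% power to detect a 50% reduction".
- 50% reduction, 80% power: 59 couples per group.

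It gives no number before losses for 90% power at a 40% reduction. It then notes that the earlier couples' cohort on which the trial is modelled "has a cumulative 16% loss to follow-up at month 12". Applying that loss to its most stringent case, it concludes: "at 90% power and 40% effect size), we therefore propose to enroll 125 couples per group for a total of 500 couples".

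Section 2.13 says that "our sample size calculations took the anticipated losses into consideration", and section 2.14 says the same. Section 2.16 says of couples who break up that "they will be censored of the study while still contributing follow-up time and visits with informative specimens".

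The amendment history records the decision to "Close study recruitment at 188 couples instead of the original 500 couples". Appendix 1 gives the reason: "Closing recruitment as we will never be able to reach the target sample within a reasonable timeframe". Neither place restates the power.

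**The concern.** If 16% of 125 couples are lost, 105 remain. That is only 8% more than the 97 the plan requires for 80% power at the same effect size. Moving from 80% to 90% power costs far more than 8%: the plan's own pair at a 50% reduction, 59 and 80, is a 36% increase. So the 125 cannot be the 90%-power number with losses covered.

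This sentence is the quantitative justification for the trial's size, and 40–50% is the effect range the plan itself calls conservative. A reader of a non-significant result would take from it a 10% chance of missing a 40% reduction. That is too low for 500 couples, and it does not apply to the 188 at which recruitment closed.

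**Working it through.** **Inputs (section 2.11 unless noted).** One-sided alpha 0.05; 97 per group (80% power, 40% reduction); 80 and 59 per group (90% and 80% power, 50% reduction); 16% loss; 125 enrolled per group; 188 couples at closure (amendment history). Normal quantiles: 1.645 (one-sided 0.05), 0.842 (80%), 1.282 (90%).

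**1. Reproducing the plan's figures.** The acquisition rate of 3.8 per 100 subject-months over 12 months gives 3.8 × 12 = 45.6 per 100. Comparing two proportions with a control risk of 0.456, one-sided with continuity correction, gives 96, 81 and 61 against the stated 97, 80 and 59. The three figures are therefore broadly reproducible. The same method needs 129 per group for 90% power at a 40% reduction before losses, and 129/0.84 = 153.6, so 154 enrolled. The 125 is not reproduced.

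**2. Scaling from the plan's own 97.** This does not require knowing the exact formula. The ratio of sample sizes for 90% against 80% power is:

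- normal quantiles: ((1.645 + 1.282)/(1.645 + 0.842))² = 1.385, so 97 × 1.385 = 134.4;
- the plan's own 50% pair: 80/59 = 1.356, so 97 × 1.356 = 131.5.

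**3. Enrolment needed for 90% power at a 40% reduction.**

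| How dropouts count | From 131.5 | From 134.4 |
|---|---|---|
| No losses | 132 | 134 |
| Half their follow-up (assumption; divide by 0.92) | 143 | 146 |
| Nothing (divide by 0.84) | 157 | 160 |

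**4. Power delivered by 125 enrolled.** For a 40% reduction, power = Φ(2.487 × √(n/97) − 1.645). For 50%, replace 97 by 59.

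| Effective n per group | 40% reduction | 50% reduction |
|---|---|---|
| 105 (125 × 0.84) | 82.7% | 95.3% |
| 115 (125 × 0.92) | 85.6% | 96.6% |
| 125 (no losses) | 88.1% | – |

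Two-sided scaling changes the 40% column little: 83.0%, 86.2% and 88.9%.

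**5. Power at closure.** 188/4 = 47 per group, assuming equal allocation, on the same four-type, per-cell basis.

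| Effective n per group | 40% reduction | 50% reduction |
|---|---|---|
| 47 (before losses) | 53.4% | 71.7% |
| 39.5 (47 × 0.84) | 47.7% | 65.1% |

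With half credit for dropouts (47 × 0.92 = 43.2), power for a 40% reduction is 50.6%.

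**The case against.** **The no-loss shortfall is small.** This stands. The variant in step 1 gives 89.3% at 125. One-sided variants that come within two couples of each of the three stated figures need 126 to 136 before losses. A two-sided, continuity-corrected variant fits less well (94, 78 and 60) and needs 122. If 97 and 80 were rounded up from just above 96 and 79, the plan's own ratio still requires 96.01 × 79.01/59 = 128.6. The main error is that the 16% loss is not covered. No variant tried reaches 125 once it is applied: even 122/0.84 is 146.

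**Couples who leave still contribute time.** Section 2.16 says so, and section 2.11 expects most transmission early, so half credit may understate their contribution. That favours the upper part of the range, but full credit still gives only 88%.

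**The 97 is itself uncertain.** It follows closely from a 45.6% control risk but not from the roughly 40% cumulative incidence in section 2.11: 0.40 against 0.24, one-sided, needs 105. On that basis power is lower, 86.1% with no losses and 80.3% at 105. Since 105/0.84 = 125, an 80%-power number may have been labelled as 90%; this is inference, and the conclusion does not depend on it.

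**The four-type basis predates Gardasil 9.** Appendix 1 claims 73.1% more analysable outcomes. Multiplying the effective size by 1.731 would move 53% and 48% to about 74% and 67%. That crude scaling ignores correlation between types and previously vaccinated participants, and the later removal of Visit 6 works the other way. Section 2.8 still defines the primary outcome on four types, and the amendment gives no revised power. The basis must be labelled, but the stated figure is not rescued.

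**The target was abandoned, and results will be read through hazard ratios and confidence intervals.** This limits the practical consequence. It does not make the stated power correct.

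**Conclusion.** The concern holds. On the plan's own per-cell basis, 125 enrolled couples per group gave about 83–86% power for a 40% reduction at one-sided 0.05, and at most about 88%. A 90% claim with 16% loss needs about 157–160 enrolled per group, or about 143–146 with half credit for dropouts. The statements in sections 2.13 and 2.14 that losses were allowed for are not true at 90% power.

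The percentages are conditional on the plan's 97 per group. Half credit for dropouts is an assumption. The figures for 188 couples also assume equal allocation and four types; they show what the section 2.11 calculation implies at that size, not a full power analysis of the nine-valent trial as run.

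**What to change.** In section 2.11, remove the statement that 125 per group corresponds to 90% power at a 40% reduction. Replace it with the following content:

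- With 125 couples enrolled per group, 16% loss and a one-sided 0.05 per-cell comparison, power was about 83–86% for a 40% reduction and about 95–97% for a 50% reduction. The lower values count dropouts as contributing nothing, the higher as contributing half their follow-up.
- At the closing size of 188 couples (about 47 per group if allocation was equal), power on the same basis is about 53% before losses and 48% after for a 40% reduction, and about 72% and 65% for a 50% reduction.
- This is the four-type calculation and predates the change to Gardasil 9.

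State the control risk behind the 97, since 45.6% and 40% give different answers. If the sponsor still has the original calculation, rerunning it with stated inputs would be better than scaling. Bring the statements on losses in sections 2.13 and 2.14 into line.

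The cost is a corrected paragraph with a less favourable power. No participants, visits or analyses change.
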